## **5.7 Adverse Reactions and Their Management**

**5.7.1 Reported Adverse or Unanticipated Events.** We do not anticipate any adverse events as a result of study participation. The RA, in collaboration and discussion with the PI, will report to the Institutional Review Board (IRB) in a timely manner any discovery of an unanticipated or adverse event. An adverse event will be reportable to the IRB if it meets the following criteria: a) affects patient safety; b) affects patient risk-benefit assessment to participating in the study; and c) affects data integrity. Study staff will report adverse events to the IRB as soon as they are discovered and discussed with the PI or designee (within 24 hours). The PI will be responsible for cataloguing and tallying adverse events, and she will report these events to the DF/HCC IRB as well as review the report with the mentors of the proposed study. Study staff will also be required to undergo NIH training in the conduct of research with human subjects prior to engaging in any research activities.

**5.7.2 Anticipated Reactions.** We do not anticipate that participants will experience any serious adverse reactions. Some participants may experience feelings of distress, sadness or emotional/physical fatigue when discussing stress and/or cancer-related topics. The PI is a licensed clinical psychologist with advanced training in clinical interviewing and assessment. Participants will be instructed to skip or decline answering any survey that they find upsetting or uncomfortable.

While this study does not target participants with depression or anxiety, it is possible that some will experience these conditions and related symptoms. The study PI is a licensed psychologist, who will evaluate and meet with any patient experiencing distress related to study participation, to determine if the patient requires further intervention.

Although we will instruct participants to maintain the confidentiality of the group by not discussing anything that goes on in the group with others, we cannot guarantee that group members will not share the content of the group with others. Extra attention will be taken during the informed consent process to explain this risk to participants. In addition, participants will be advised to wear headphones and sit in a quiet place to protect their own, and other group members', privacy.

**5.7.3 Reaction Management.** If, during the course of the study, study participants become distressed, the PI will be available to discuss the patient's concerns. If any aspects of the study make the participant very upset, appropriate follow-up action will be taken by the PI who will assess for safety and make appropriate referrals for treatment (e.g., MGH oncology social services). [name], a clinical psychologist with extensive experience working with cancer patients, will consult with the study team on complicated situations involving psychological distress at team meetings or as needed.

## **6.0 STATISTICAL ANALYSIS**

This study will assess the feasibility and acceptability of the 3RP-AYA among approximately 72 adolescent and young adult cancer survivors who are within 5 years post-treatment.

### **6.1 Primary and secondary endpoints.**

The primary study endpoints are the feasibility and acceptability of the program for adolescent and young adult cancer survivors who are within 5 years post-treatment completion. These will be detailed further below in the data analysis section.

### **6.2 Sample Size and Power Calculations.**

This phase of the study is designed as a pilot RCT and thus is exploratory. Though our analyses are not powered to detect an effect, the aim of this pilot is to adapt and test the feasibility and acceptability of a mind-body based stress management program. Our emphasis on establishing feasibility and acceptability is consistent with best practices in treatment development. The sample size chosen provides sufficient power for the primary outcome and feasibility of the intervention based on enrollment and intervention session attendance ( $\geq 6$ .) Our sample size of 72 allows us to account for study attrition (nonparticipation after signing study consent, as defined by not participating in any 3RP sessions), with the goal of having 60 active participants. We consider a 75% session completion rate (approximately 6 out of 8 sessions) as a threshold for establishing intervention feasibility. With a sample size of 60 3RP-AYA, we would have 90% power to demonstrate a mean participation rate 5.5% higher than the threshold with a one-sided significance level of 0.05, assuming the SD of participation rate is 10%. Therefore, we believe our sample size of 72 will be sufficient to answer our questions about feasibility and acceptability.

**6.3 Stratification factors and intervention allocation plan for randomized studies.** Participants will be randomized to the 3RP-AYA immediate start group (IG) or waitwait-list control group (WG) using a random plan generator. While we considered stratifying by gender, age and cancer type, we chose not to given our proposed sample size and the limited a priori evidence to suggest there would be differential effects on our proposed treatment outcomes.

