## 5.0 STUDY DESIGN AND METHODS

### 5.1 Design / Study Type

This is a pilot RCT to examine the feasibility and acceptability of the 3RP-AYA among approximately 72 adolescent and young adult cancer survivors who are up to 5 years post-treatment. Participants who complete the baseline questionnaire and are randomized will be enrolled and counted toward the accrual goal of 72. As such, up to 72 participants may be enrolled in the study in order to allow approximately 60 patients to participate total in the intervention and waitlist arms (goal of 30 completer-participants per arm). Participants do not need to complete every study measure to be counted towards the 72-participant accrual goal (i.e., participants who only complete some measures/3RP-AYA sessions will still be counted towards the accrual goal); however, patients who do not complete any of the study measures or who do not participate in any intervention visits will not be counted towards this goal.

We plan to examine the proportion of patients who are eligible and the proportion who are found to be ineligible due to age, language, inability to use the videoconferencing software, oncologist refusal, and medically or psychiatrically unable to participate. Out of those who are eligible, we will examine the proportion of enrollments, refusals, lost-to-follow up, withdraws, and study completers. We will examine reasons for and rates of ineligibility and refusal, as these will inform the feasibility of the study and of delivering the program virtually. We will also examine the characteristics of non-completers and the circumstances of non-completion.

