## **6.8 Analysis Plan.**

### **6.8.1 Aim a) To examine the feasibility and acceptability of a group-based, stress-management and resiliency intervention delivered via videoconferencing technology for adolescent and young adult cancer survivors who are within 5 years of having completed cancer treatment.**

Descriptive statistics, including means, frequencies, and ranges will be used to describe the sample and to summarize feasibility, acceptability, and program satisfaction. Feasibility outcomes will be assessed by determining the proportion of individuals who were recruited, screened, and enrolled in the study. Response frequencies will summarize reasons for ineligibility and refusal. We will also determine the proportion of enrolled participants who complete the study. Participants who complete at least 75% of the treatment sessions (6 out of 8 sessions) will be identified as treatment completers. We will examine the proportion of individuals who attend each session and the percent that adhere to recommended RR practice (defined as RR elicitation at least 3 days/week). For acceptability, response frequencies will summarize quantitative feedback on the 3RP-AYA Acceptability Questionnaire (Appendix 8.15). Together with qualitative feedback from the Exit Interviews (Appendix 8.29) and Expert Interviews (Appendix 8.30), this information will be used to inform the feasibility and acceptability of the intervention.

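### The power statement in section 6.2 does not follow from its own inputs: 60 participants and an SD of 10% give about 99.5% power for 5.5 points, not 90%

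*Combined protocol and SAP*

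**What the plan says.** Section 6.2 sets 75% session completion, about 6 of 8 sessions, as the feasibility threshold. It enrols 72 so that 60 are active after attrition, and for those 60 it states: "we would have 90% power to demonstrate a mean participation rate 5.5% higher than the threshold with a one-sided significance level of 0.05". The calculation takes 10% for the standard deviation of individual attendance. The section then concludes that 72 is enough. Earlier in the same paragraph it says: "The sample size chosen provides sufficient power for the primary outcome". No test is named.

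Section 5.1 splits the 60 across the two arms, with a "goal of 30 completer-participants per arm". Section 6.8.1 analyses feasibility without a hypothesis test: "Descriptive statistics, including means, frequencies, and ranges will be used to describe the sample and to summarize feasibility, acceptability, and program satisfaction".

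**The concern.** Sample size, SD, significance level and difference together determine power, so the stated 90% can be checked directly. It fails the check by a wide margin: the implied chance of missing a 5.5-point excess is about 0.5%, not 10%.

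What is at stake is the credibility of the sample-size justification, not its conclusion. This sentence is the only quantitative support for calling 72 adequate, and a reader who finds the mismatch cannot tell which of the four figures is wrong. Someone planning the later efficacy trial mentioned in section 6.8.2 could also carry forward a wrong relation between sample size, SD and detectable difference.

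**Working it through.** **Inputs, all from section 6.2 unless noted**

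- n = 60 active participants, both arms pooled (72 enrolled)
- Threshold 75%
- Difference δ = 5.5%, read as percentage points (80.5% against 75%)
- SD = 10 percentage points
- One-sided α = 0.05
- Stated power 90%
- Variant only: 30 completers per arm (section 5.1)

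**Method.** A mean rate, its SD and a fixed threshold point to a one-sample t-test. Participants are taken as independent.

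- Noncentrality: λ = δ√n / SD
- Power = P(T > t₀.₉₅,ₙ₋₁), where T is noncentral t with n − 1 degrees of freedom and noncentrality λ
- Normal approximation: power = Φ(λ − 1.645); difference with 90% power = (1.645 + 1.282) × SD / √n

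**Step 1: the plan's own figure.** λ = 5.5 × √60 / 10 = 4.26 and the critical value is 1.671. Power = 99.5% (t, 99.49%; normal, 99.55%). The stated 90% is not reproduced.

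**Step 2: the difference that does have 90% power.** Normal: 2.926 × 10 / √60 = 2.926 × 1.291 = 3.78 points. Noncentral t: 3.82 points. The plan states 5.5.

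**Step 3: other readings of the sentence**

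| Reading | Power (t unless noted) |
|---|---|
| 5.5% relative to 75% (0.055 × 75 = 4.125 points), one-sided | 93.5% |
| 5.5 points, two-sided 0.05 | 98.7% |
| 4.125 points, two-sided 0.05 | 88.2% |
| All 72 enrolled, 5.5 points, one-sided | 99.9% (90% power at 3.5 points) |
| Two-sample, 30 per arm, one-sided | 67.7% |
| One-sample test of a proportion, 80.5% against 75%, n = 60 | 23.5% (normal) |

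The third row comes near 90% but contradicts the stated one-sided level. None of these readings keeps every stated input and gives 90%.

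**Step 4: what would reproduce 90% and 5.5 points**

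- n = 30, SD 10: λ = 5.5 × √30 / 10 = 3.01, critical value 1.699, power 90.3%; the difference with 90% power is 5.47 points, which rounds to 5.5.
- n = 60, SD about 14.4: power 90.0%.
- n = 60, SD 10, design effect about 2.02: with groups of 8 (section 5.3), 1 + 7 × ICC = 2.02 gives an ICC of about 0.146. Section 6.2 states no such allowance.

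**Step 5: sensitivity to the SD.** The 10% has no stated source, and the other SDs here are assumptions. At n = 60 the difference with 90% power is 3.8 points at SD 10, 5.4 at SD 14 and 7.6 at SD 20. For orientation, if the 8 sessions were attended independently, binomial variation alone would give an SD of √(0.75 × 0.25 / 8) = 15.3 points at 75% and √(0.805 × 0.195 / 8) = 14.0 points at 80.5%.

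**The case against.** The arithmetic is not in dispute; the objections concern interpretation and weight.

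- **Direction.** Saying that power is understated assumes that the SD of 10% is the correct input. If the SD was meant to be about 14.4%, then 90% and 5.5 points are right for 60 participants and nothing is understated. The binomial range of 14.0 to 15.3 points makes that as credible an origin as a calculation for 30 participants. This stands. Both origins are inferences, and the direction holds only on the stated inputs.
- **Remedy.** Writing in 3.8 points could make matters worse if the SD is the misreported figure: at SD 14.4, power for 3.8 points with 60 participants is about 65%. This also stands, so the sponsor should trace the calculation before settling the wording.
- **Independence.** Sessions run in groups of up to about 8, and clustering could lower the effective sample size. But the plan claims no clustering allowance, so this does not explain its figure.
- **Weight.** The pilot is described as exploratory and not powered to detect an effect, and no test against 75% is planned. This limits the point to a minor one. It does not remove it, because the plan chose to state a power calculation and rests its conclusion on it.

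**Conclusion.** The concern holds, as a minor point. On the stated inputs (60 participants, SD 10 points, one-sided 0.05), power for 5.5 points is about 99.5% rather than 90%, and 90% power applies to about 3.8 points. This rests on a one-sample t-test and independent participants, neither of which section 6.2 states.

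Which figure is wrong cannot be settled from the documents. Whichever single figure is corrected (sample size, difference, power or SD), 60 active participants keep about 90% power or more for 5.5 points. The conclusion that 72 is enough is therefore not overturned, and no participant number, planned analysis or result changes. An SD well above 14% would be a different matter, but nothing in the plan indicates one.

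**What to change.** Trace the original calculation, then rewrite the one sentence in section 6.2. Name the test and write percentage points. If the stated inputs are right, suitable wording is: with 60 active participants, an SD of 10 percentage points and a one-sample, one-sided 0.05 t-test, there is 90% power for a mean participation rate 3.8 percentage points above 75% (99.5% power for 5.5 points). If another input was misreported, correct that one instead: say so if the calculation was for 30 participants, or give the intended SD if it was about 14.4%.

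Optionally, because the SD has no stated source, add one line labelled as assumption: with 60 participants and 90% power, the difference is 5.4 points at SD 14% and 7.6 points at SD 20%.

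The cost is one sentence, or two with the optional line. The target of 72 stays, and no extra participants, data or analyses are needed.

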### **6.5 Stratification factors and their impact on design.** N/A

### **6.6 Early stopping rules, if appropriate.** N/A

**6.7 Definition of and allowance in design for unevaluable/ineligible participants.** No unevaluable and/or ineligible participants will be included in this study.

## **6.8 Analysis Plan.**

### **6.8.1 Aim a) To examine the feasibility and acceptability of a group-based, stress-management and resiliency intervention delivered via videoconferencing technology for adolescent and young adult cancer survivors who are within 5 years of having completed cancer treatment.**

Descriptive statistics, including means, frequencies, and ranges will be used to describe the sample and to summarize feasibility, acceptability, and program satisfaction. Feasibility outcomes will be assessed by determining the proportion of individuals who were recruited, screened, and enrolled in the study. Response frequencies will summarize reasons for ineligibility and refusal. We will also determine the proportion of enrolled participants who complete the study. Participants who complete at least 75% of the treatment sessions (6 out of 8 sessions) will be identified as treatment completers. We will examine the proportion of individuals who attend each session and the percent that adhere to recommended RR practice (defined as RR elicitation at least 3 days/week). For acceptability, response frequencies will summarize quantitative feedback on the 3RP-AYA Acceptability Questionnaire (Appendix 8.15). Together with qualitative feedback from the Exit Interviews (Appendix 8.29) and Expert Interviews (Appendix 8.30), this information will be used to inform the feasibility and acceptability of the intervention.

### **6.8.2 Exploratory Aim b) We will examine the preliminary effects of the intervention on psychosocial measures of fatigue, mindfulness, depressed mood, anxiety, and stress.**

Preliminary outcome data may be used to inform future assessment instruments and methods. We may also conduct exploratory hypothesis testing to examine preliminary changes in our proposed intervention targets (changes in psychosocial outcomes, including mindfulness, depressed mood, anxiety, stress). A priori statistical tests of intervention-related changes will be planned for a future efficacy trial of this intervention.

First, we will examine the frequency distributions of all variables. Potential variables of interest (e.g., gender, history of RR practice) will be included as covariates if they are significantly correlated with each outcome of interest at  $p < .25$ . We will compare the baseline characteristics of completers vs. study non-completers. The primary analysis will be a completer analysis limited to those with complete data, and we will conduct a sensitivity analysis using multiple imputation for missing data.

First, we will examine between group differences in change scores in our exploratory psychosocial outcomes from enrollment (T0) to T1 (post-treatment for IG, 3-months post-enrollment/baseline #2 for WG). To further explore preliminary efficacy, we will evaluate within-group change from pre- to post-intervention (using T0 to T1 data for the IG and T1 to T2 data for the WG) for each condition separately, and then for both groups combined. Finally, within the IG only, we will explore potential maintenance of intervention benefits with a repeated measures ANOVA, including the 3 survey timepoints.

Exit interviews (Appendix 8.29) will be audio-recorded and transcribed; NVIVO software will be utilized in the thematic analysis, which will be led by members of the study staff under the mentorship of [name]. Coders will meet on a weekly basis to discuss the coding framework, categories, and coding plan. To ensure coding reliability, coding discrepancies will be resolved through discussion and comparison of raw data. Coding will continue until a high level of reliability ( $Kappa = >0.80$ ) is established.

Expert interviews (Appendix 8.30) will be audio-recorded and transcribed; rapid coding will be utilized in the thematic analysis, which will be led by members of the study staff under the mentorship of [name]. Coders will meet on a weekly basis to discuss the coding framework, categories, and coding plan. To ensure coding reliability, coding discrepancies will be resolved through discussion and comparison of raw data. Coding will continue until consensus has been reached.

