## 4.2 The Informed Consent Process & Enrollment

A member of the study staff will determine patients' eligibility status, explain the purpose of the study and study procedures, and answer any questions prior to completing informed consent. During the informed consent discussion, study staff will carefully review the informed consent document with the patient.

All patients will be provided with study staff contact information if any questions or concerns regarding the research arise. In addition, all patients will be explicitly informed that Partners Telehealth services provides

secure HIPAA-compliant videoconferencing software. We will explain that although we will do our best to ensure confidentiality on our end, we cannot guarantee 100% that other group members will not share the content of the group. Patients will also be advised to wear headphones and sit in a quiet place during the virtual study visits to protect their own, and other group members', privacy. Participants will also be informed that after signing the informed consent, they will complete a brief test call with a study staff member using the videoconferencing software in order to ensure proficiency with the software. If a participant completes a study questionnaire and is later deemed ineligible, their responses will be exempt from data analysis. Subjects who are found to be unable to use the videoconferencing software during the brief test call will be considered ineligible for the study.

For eligible patients, a trained member of study staff with a bachelor's-level training or greater will obtain informed consent in one of three ways: 1) in-person, 2) electronically, or 3) via phone and mail correspondence, in accordance with patient preferences and availability, prior to participating.

**4.2a In-person Informed Consent Process:** Study staff will go through the informed consent discussion detailed above in a private room to protect patient confidentiality and answer any questions. Upon consent, study staff will maintain one copy of the informed consent form for study records, and participants will be instructed to maintain one copy for personal reference. Patients who would like more time to consider participation during in-clinic approach are able to take the forms home with them to review, and if interested, they may complete the consent process electronically (4.2b) or proceed to mail back the consent forms (see 4.2c).

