Rationale for hair cortisol versus salivary cortisol. Recent studies comparing salivary vs. hair cortisol have found that hair samples provide a more robust measure of chronic stress. Specifically, hair cortisol provides a more complete snapshot of cortisol concentration levels across longer periods (e.g., over 3 months) whereas salivary cortisol captures the acute stress response. As such, studies have been more likely to find changes in hair cortisol levels in response to stress management programs. Further, hair sampling may be less burdensome, invasive, and easier to collect than saliva sampling, which requires subjects to provide several samples throughout the day. Saliva sampling is also subject to sampling errors due to incorrect timing, inefficient sampling, and inaccurate collection procedures. We will collect feedback and perceptions of hair sampling measures at study completion. **Sample Processing:** Hair cortisol will be processed by [name] laboratory at the University of Massachusetts, Amherst. Prior to shipping, samples will remain wrapped in aluminum foil, labeled with a study ID and stored at room temperature in a padded envelope.

**5.2.3b Psychosocial Measures.** We will gather relevant information related to current or past levels of distress from participants to examine the psychosocial impact of this program. Information that will be

collected from participants will include symptoms of stress, worrying, anxiety, and depression (Appendix 8.17). These measures take approximately 35 minutes to complete. Participants have the option to skip any questions they prefer not to answer.

- Patient-Reported Outcomes Measurement Information System (PROMIS) Measures: PROMIS is a set of person-centered measures that evaluates and monitors physical, mental, and social health in adults and children. A variety of subscales will be used as exploratory outcomes including, PROMIS Anxiety PROMIS ED Anxiety – short form 4a, PROMIS ED depression – short form 4a, PROMIS ED anger – short form 5a, PROMIS fatigue short form 7b, PROMIS sleep disturbance short form 8a, PROMIS Social Isolation short form 4a
- Coping Self-efficacy Scale: The Coping Self-Efficacy Scale (CSES) is a 26-item measure of perceived self-efficacy for coping with challenges and threats.

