### **5.3 Randomization and Treatment Delivery.**

Following completion of the baseline survey, participants will be randomized to the immediate start resiliency intervention group (IG) or waitlist control group (WG). Randomization will be conducted using a random plan generator. Groups will consist of up to approximately 8 participants. We will run approximately 6 or more separate intervention and waitlist control groups, for a total of 72 survivors. [name], a psychology trainee in the BMED internship program, or a pre-doctoral medical student, all under the supervision of [name] as study staff, will lead the group sessions, some of which will be audio-recorded for fidelity. Medical students will not under any circumstances conduct consent in their role as study staff. Prior to running the groups, [name] will train study staff on the study protocol, and we will have weekly supervision meetings to provide feedback and ensure fidelity. To decrease participant burden and extend reach, both groups will be delivered via MGH Telehealth (as successfully done in our sister protocols: DF/HCC #17-063 & DF/HCC #17-315).

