## 5.5 Data Collection and Storage.

Prior to study enrollment, study data will be collected via medical record review for Partners patients or through patient self-report, if no available EMR through the Partners Healthcare System, at screening to determine study eligibility. In addition, we will gather descriptive information about our sample via brief surveys and assess levels of the stress hormone cortisol via hair sample collection. Specifically, we will collect data on:

Data	At Screening	At Baseline	At 3RP	At Post-3RP	At 3-Month Follow-Up
Date of birth	x				
Gender	x				
Languages spoken	x				
Cancer diagnosis	x				
Date of diagnosis	x				
Treatment type(s)	x				
Date of treatment completion	x				

Data	At Screening	At Baseline	At 3RP	At Post-3RP	At 3-Month Follow-Up
Demographic factors		x			
Psychosocial measures:					
Visual Analog Scales		x		x	x
Intolerance of Uncertainty Scale		x		x	x
Measure of Current Status – Part A (MOCS-A)		x		x	x
Patient-Reported Outcomes Measurement Information System (PROMIS) Measures		x		x	x
Coping Self-efficacy Scale		x		x	x
Health Behavior Questions		x		x	x
Penn State Worry Questionnaire (PSW-Q)		x		x	x
Interpersonal Reactivity Index		x		x	x
Current Experiences Scale (CES)		x		x	x
Hair cortisol measurement		x		x	
3RP acceptability questionnaire				x (intervention arm only)	x (waitlist arm only)
Weekly RR practice logs (Appendix 8.27)			x		
COVID19 Supplementary Questions		x		x	x
Optional Exit Interview (Appendix 8.29)					x (after completion of all study measures)

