### **6.9 Handing of missing data in the analysis.**

This study is intended to test the feasibility and acceptability of the stress management program. We will explore differences between study completers and non-completers on patient demographic and other relevant variables to inform the next phase of this trial. We will assess whether the mechanism of missing data is missing at random. We will perform sensitivity analysis using: 1) a completer analysis limited to those who have complete data and 2) multiple imputations for missing data. To address missing data at follow-up, participants who are no longer interested in participating in the 3RP-AYA sessions will still be given the option to complete follow-up assessments.

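### Sections 6.8.2 and 6.9 disagree on the lead analysis of the exploratory T0–T1 comparison, and its complete-data set is undefined

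*Combined protocol and SAP*

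**What the plan says.** The comparison at issue is the between-arm difference in T0-to-T1 change on the psychosocial measures. It is hypothesis 2.2a in the objectives and appears as Exploratory Aim b in section 6.8.2.

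- **Section 6.8.2** sets the lead: "The primary analysis will be a completer analysis limited to those with complete data". Multiple imputation is the sensitivity analysis. The sentence covers every psychosocial analysis in the section: the T0–T1 contrast, within-group change, and the three-timepoint ANOVA in the immediate arm.
- **Section 6.9** says: "We will perform sensitivity analysis using: 1) a completer analysis limited to those who have complete data", with multiple imputation as the second item. No lead is named.
- **Section 6.8.1** has the only explicit definition of a completer: at least 6 of the 8 sessions.
- **Section 5.2.3b**: "Participants have the option to skip any questions they prefer not to answer". **Section 5.7.2**: "Participants will be instructed to skip or decline answering any survey that they find upsetting or uncomfortable". No rule says when a scale with skipped items still counts as complete.
- **Section 5.3** places randomisation after the baseline survey. **Section 4.2** removes people later found ineligible: "If a participant completes a study questionnaire and is later deemed ineligible, their responses will be exempt from data analysis".
- **Section 6.9** also keeps follow-up open after sessions stop: "participants who are no longer interested in participating in the 3RP-AYA sessions will still be given the option to complete follow-up assessments".

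No section states the population to which imputation applies. The accrual rule in 5.1 and the statement on unevaluable participants in 6.7 do not define an analysis set.

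**The concern.** One analysis has two roles, and its membership is left open. Completeness could mean T0 and T1 for one outcome, all three timepoints, or something wider. If the choice is made after the data are seen, neither the estimate nor its denominator is reproducible from the plan.

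Randomisation follows the baseline survey, so most loss from this contrast arises after assignment, while only the immediate arm is attending sessions. Restricting to people with complete data then selects on a post-randomisation event. If that selection works differently in the two arms, the comparison is no longer protected by randomisation and can be biased in either direction. If loss is equal and equally related to outcome in both arms, the bias is zero.

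At stake is the preliminary-effect estimate that would be carried to a future trial. The feasibility and acceptability endpoints do not depend on it.

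**Working it through.** The plan gives no T1 loss rate and no complete-data sample size, so there is no figure of its own to reproduce. The check has a reading part and an arithmetic part.

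**Reading.** Section 6.8.2 makes the complete-data analysis the lead; 6.9 makes it a sensitivity analysis. The labels cannot both stand as written. The attendance definition in 6.8.1 cannot fill the gap: the waitlist arm has had no sessions by T1, so nobody in it could qualify.

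**Inputs for the size of the bias**
- 72 enrolled with a goal of 60 active participants (section 6.2): 1 − 60/72 = 16.7%. In 6.2 this allowance is for people who attend no session. Using it as a T1 loss rate m is an assumption; 10% and 25% are shown beside it.
- Assumed: T0–T1 correlation r = 0.5 to 0.7; correlation ρ = 0.3 to 0.4 between loss and the stated variable in one arm; random loss of the same share in the other arm; no true effect; bivariate-normal scores with equal variances.
- Unit: SD of the change score.

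**Standard error.** √(2/n) per contrast: √(2/36) = 0.24 and √(2/30) = 0.26.

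**Loss related to T0 in one arm, unadjusted change scores in people with complete data.** The correlation of T0 with change is −√((1−r)/2). The absolute bias is ρ·k·√((1−r)/2), with k = φ(z)/(1−m) and z the normal quantile of m.
- m = 10%: k = 0.195, bias 0.023 to 0.039
- m = 16.7%: k = 0.300; smallest 0.3 × 0.300 × √0.15 = 0.035, largest 0.4 × 0.300 × √0.25 = 0.060
- m = 25%: k = 0.424, bias 0.049 to 0.085

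Simulation with 36 per arm and 20,000 runs per scenario agrees: 0.036 to 0.061 at 16.7% loss. With equal T0-dependent loss in both arms the bias is 0.000.

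**Same loss, conditioning on T0.** A likelihood model using all observed T0 and T1 values is off by at most 0.002 at 16.7% loss and at most 0.005 at 25%. With a further 5% of T0 scores missing at random, the figure at 16.7% loss is at most 0.006. A complete-data analysis with T0 as a covariate is off by at most 0.007, about simulation noise. The gain therefore comes from conditioning on T0, not from imputation as such.

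**Loss the fix does not cure, m = 16.7%**
- Loss tied to the change itself: 0.09 to 0.12 with complete-data change scores (ρ·k), still about 0.07 to 0.10 after conditioning on T0.
- Loss tied to the unseen T1 score: about 0.04 to 0.06 with complete-data change scores, about 0.06 to 0.09 after conditioning on T0. Here the fix is somewhat worse.

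**The case against.** The strongest reply has four parts.

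1. **The conflict changes little.** Section 6.8.2 is the specific section and can be taken to govern, with 6.9 read as comparing two approaches. Both analyses are run either way. That is a fair practical reading, but the labels still disagree, and the set and the imputation population stay undefined.
2. **The natural meaning is clear.** A T0–T1 change score needs T0 and T1 for that outcome. If each is unscorable 1–3% of the time independently (an assumption), 60 people returning both surveys leave 60 × (1−p)², or 56 to 59. A reader might infer a far smaller lead sample by requiring all nine psychosocial instruments listed in section 5.5: 60 × (1−p)¹⁸ gives 35 to 50, and across three timepoints 60 × (1−p)²⁷ gives 26 to 46. The documents do not support that reading. Section 6.8.2 assigns timepoints to each analysis and speaks of each outcome separately, and skipping that clusters in the same people would shrink the gap. This part stands, and those counts should not be used as the size of the problem.
3. **Imputation is not the cure.** This also stands. With T0 observed, a T0-adjusted analysis of people with T0 and T1 removes the same bias. Section 6.8.2 may bring in covariates correlated with the outcome at p < .25, but it does not name the T0 score, so that adjustment is not assured.
4. **No analysis wins under every mechanism.** Correct, as the last lines of the working show. It is a reason to report both, not to leave the lead unsettled.

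**Conclusion.** The point holds as a contradiction to reconcile, an undefined set, and a cheap improvement to the lead analysis. The bias that conditioning on T0 can repair is about 0.04–0.06 SD of change at 17% loss, at most about a quarter of one standard error. That size rests on assumed loss rates and correlations, and on loss related to T0 in one arm only; nothing in the documents shows that such loss will occur.

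The rating is minor. Section 6.2 says the analyses are not powered to detect an effect; 6.8.2 makes testing optional and leaves a priori tests to a later efficacy trial.

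Two stronger inferences should be resisted. A reader might conclude that the trial's main result is compromised; it is not, because the primary endpoints are feasibility and acceptability. A reader might also take the 6.8.2 lead to be a per-protocol analysis of people with at least 6 sessions; its own qualifier refers to data, not attendance, so the text does not establish that.

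**What to change.** In both 6.8.2 and 6.9, name one lead analysis for the T0–T1 comparison:

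- **Set:** all eligible randomised participants in their assigned arm, regardless of session attendance or T2 completion, keeping the section 4.2 exemption for people later found ineligible.
- **Method:** condition on that outcome's T0 score. Use a baseline-adjusted or likelihood-based mixed model on all observed T0 and T1 values, or the multiple imputation already planned, with this set stated as the imputation set.
- **Supplementary:** keep the complete-data analysis, defined per outcome as observed T0 and T1 and not by attendance.
- **Reporting:** give T1 loss by arm, show both estimates, and state that neither removes bias from loss tied to the unseen T1 score or to the change itself.

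The cost is wording in two sections and slightly more analysis work. No extra data are needed, since 6.9 already offers follow-up assessments to people who stop sessions. The downside is that if loss depends on the unseen T1 score, the T0-conditioned estimate can be the more biased of the two, which is why both should be reported.
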